## Specific Aims

Our goal is to measure the impact of timing of postpartum contraceptive implant insertion on breastfeeding success and duration and to explore women's experiences with and attitudes towards contraceptive and breastfeeding counseling in the peripartum time period.

Specific Aim 1: To compare time to lactogenesis stage II among women randomized to receive the contraceptive implant within 30 minutes postpartum, 1-3 days postpartum and 6 or more weeks postpartum, utilizing a validated measure

Specific Aim 2: To assess rates of breastfeeding continuation, exclusivity, and satisfaction as well as device continuation and method satisfaction at 6 months postpartum among women who were randomized to receive the contraceptive implant within 30 minutes postpartum, 1-3 days postpartum and 6 or more weeks postpartum, utilizing a validated measure

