## **Research Design and Methods**

### *Research Design and Study Subjects*

This will be a three-armed randomized non-inferiority study of women delivering at the Weiler Hospital of the Albert Einstein College of Medicine who plan to breastfeed, have known risk factors for low milk supply, and who intend to use the contraceptive implant postpartum. Women will be randomized to one of three groups: device placed within 30 minutes of placental delivery, 24-72 hours postpartum, or 6 or more weeks postpartum. All study activities will adhere to the CONSORT guidelines for reporting randomized trials. Women will be assessed at enrollment, 1-5 days postpartum, 6 weeks, 3 months and 6 months postpartum.

Eligibility Criteria will include:

- 1) Live pregnancy of at least 24 weeks gestation
- 2) Intention to use a contraceptive implant postpartum
- 3) Intention to use a non-hormonal bridging method of contraception until a contraceptive implant can be placed
- 4) 18 years of age or older
- 5) English or Spanish speaking
- 6) Women will be enrolled either during prenatal care or upon admission to Labor and Delivery.
- 7) Absence of pain. Among women who are being enrolled on Labor and Delivery MUST fall into one of the three following categories:

- Women presenting for induction of labor. Women will be approached and enrolled prior to the onset of labor.
- Women presenting for a planned cesarean delivery. Women will be approached and enrolled prior to entry into the operating room.

- Women who have an Epidural in place for management of pain. Prior to engaging in a discussion regarding the study protocol, women will be asked if they are experiencing any pain, and if the answer is yes, they will not be eligible for entry into the study.

7) Presence of at least one of the following conditions known to be a risk factor for low milk supply:

- Expected delivery prior to 37 weeks
- Obesity (pre-pregnancy BMI >35)
- Polycystic Ovarian Syndrome
- Diabetes (gestational or pre-gestational)
- Self-reported difficulty with low milk supply in past

*Setting and Population*

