Women will be enrolled, consented and randomized on Labor and Delivery, prior to delivery. The study brochure will be included in the standard educational materials provided to all women on admission to Labor and Delivery. All enrollment and screening will be done in private labor and delivery rooms and all measures will be taken to ensure patient privacy. Women will be explicitly told that their participation in this trial is voluntary and that they have the option of receiving a contraceptive implant at any of the time points included in this study if they decline participation in this trial. Only co-investigators who have completed CITI training and who are intimately familiar with the study protocol will be approaching or enrolling patients into the trial.

During the informed consent process, women will receive standardized contraceptive counseling, including information about the contraceptive implant and its potential effects on breastfeeding. Women who are eligible for the trial and interested in participating will be enrolled and randomized in a 1:1:1 ratio to one of the three groups to determine their timing of contraceptive implant placement. Participants will be assigned using computer-generated random numbers in blocks of varying sizes with strict allocation concealment using sequentially numbered opaque envelopes. Women will be informed of their randomization group at the time of enrollment into the trial.

Women randomized to receive the implant within 30 minutes of delivery will have the implant placed in the delivery room or operating room within 30 minutes of placental delivery. Placement of the implant will not interfere with any skin-to-skin interactions that are currently routinely encouraged for the mother and infant after every delivery. Women randomized to receive the implant within 1-3 days of delivery will have their implant placed on the postpartum unit more than 24 hours after delivery, but prior to discharge from the hospital. Women randomized to receive the implant at 6 or more weeks postpartum will be scheduled for an outpatient visit with the family planning clinic at 6-8 weeks postpartum for implant placement.

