#### *Sample Size*

To achieve specific aim 1, we chose a non-inferiority margin of an additional 8 hours to achieve lactogenesis II, as this would be clinically relevant. In order to achieve 80% power, using a one-sided Type 1 error of 5%, and with a standard deviation in time to lactogenesis of up to 18 hours, 63 women would be needed in each group, for a total of 189 women.

To achieve specific aim 2, larger sample size will be required. Prior studies in our population have found that breastfeeding continuation rates at 6 months postpartum are 27%. Assuming a non-inferiority margin of 15%, to achieve 80% power using a one-sided Type 1 error of 5%, we would need to enroll 109 women per group, for a total of 327 women total. Assuming a 15% loss to follow up rate, we will enroll 375 women total, 125 in each group. This recruitment goal will be met over an 18 month time period and is attainable based on the approximately 60 implants placed each month on the Labor and Delivery and Postpartum units.

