#### *Analysis Plan*

The following outcomes will be evaluated using T-tests and include: exclusive breastfeeding continuation, any breastfeeding continuation, implant continuation. Additional secondary outcomes include side effects and tolerability of the implant, vaginal bleeding patterns, and contraceptive use. To evaluate these secondary outcomes between the two groups we will use the T-test, Wilcoxon Rank Sum test, Chi-squared test, or Fisher's exact test as appropriate.

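### The 6-month breastfeeding comparison is powered for non-inferiority, but the Analysis Plan's T-tests are not tied to the 15-point margin; adjusting for the five entry risk factors would be an optional extra

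*Combined protocol and SAP*

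**What the plan says.** Specific Aim 2 is "To assess rates of breastfeeding continuation, exclusivity, and satisfaction as well as device continuation and method satisfaction at 6 months postpartum" across the three timing groups. The Sample Size section takes from earlier work in this population that "breastfeeding continuation rates at 6 months postpartum are 27" per cent, and then sets the design: "Assuming a non-inferiority margin of 15%, to achieve 80% power using a one-sided Type 1 error of 5" per cent. This leads to 109 per group, and 125 per group are to be enrolled to allow for 15% loss.

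The Analysis Plan, the only analysis section, reads: "The following outcomes will be evaluated using T-tests and include: exclusive breastfeeding continuation, any breastfeeding continuation, implant continuation". For the additional secondary outcomes it says "we will use the T-test, Wilcoxon Rank Sum test, Chi-squared test, or Fisher's exact test as appropriate", and that sentence speaks of two groups although the trial has three arms. It names no margin, one-sided level, confidence bound, reference arm or covariate.

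Two other places bear on adjustment. The eligibility list in Research Design and Study Subjects requires "Presence of at least one of the following conditions known to be a risk factor for low milk supply" and names five. The Recruitment section says "Participants will be assigned using computer-generated random numbers in blocks of varying sizes" and names no stratification factor.

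**The concern.** The design and the sample size are non-inferiority; the analysis sentence is a bare T-test. Read in the usual way, that test asks whether the difference is zero. Failing to show a difference is not the same as showing that the deficit is below 15 points. If a non-significant result were taken as support for early placement, the chance of accepting a truly inferior timing would not be held at the 5% on which the sample size rests. Because no reference arm is stated, the plan also leaves open which differences are to be read against the margin.

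A smaller matter is precision. The five entry conditions are fixed before randomisation and are natural covariates. If they predict breastfeeding at 6 months, adjusting for them would tighten the bound a little. The documents do not say that they do, and do not say that all five are recorded for every woman.

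**Working it through.** **Inputs from the documents.** Rate 27%, margin 15%, one-sided 5%, 80% power, 109 per group, 125 enrolled per group, 15% loss (Sample Size). Evaluable per arm: 125 × 0.85 = 106. The margin is read as absolute percentage points, because that reading reproduces 109. Normal approximations are used throughout.

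**1. The plan's own figure.** With equal true rates, n = 2 × 0.27 × 0.73 × (1.6449 + 0.8416)² / 0.15² = 108.3, so 109. It reproduces.

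**2. Power at 106 per arm, unadjusted.** SE = √(2 × 0.27 × 0.73 / 106) = 0.0610. Power = Φ(0.15/0.0610 − 1.645) = Φ(0.815) = 79.2%. The one-sided 95% half-width is 1.645 × 0.0610 = 10.0 points.

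**3. An ordinary T-test at the margin.** Let the true rates be 27% and 12%, a 15-point deficit.
- SE = √((0.27 × 0.73 + 0.12 × 0.88)/106) = √(0.3027/106) = 0.0534, and 0.15/0.0534 = 2.807.
- Probability of non-significance, two-sided 5%: Φ(1.960 − 2.807) = Φ(−0.847) = about 20%.
- The same at a one-sided 5% level: Φ(1.645 − 2.807) = Φ(−1.162) = about 12%.
- Probability that a one-sided 95% lower bound lies above −15 points: 5% by construction.

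The two rules also disagree on the observed result. With the SE of step 2, the bound rule needs an observed deficit below 15 − 10.0 = 5.0 points. The two-sided T-test stays non-significant up to 1.96 × 0.0610 = 12.0 points. Between about 5 and 12 points the test finds no difference although non-inferiority has not been shown.

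**4. The optional adjustment.** R², prevalences and effect pattern are all assumptions, since the documents give none. Prevalences for preterm, BMI, PCOS, diabetes and past low supply are 20, 40, 10, 40 and 25%, before requiring at least one factor. Log-odds ratios are in the ratio 0.5 : 1 : 0.5 : 0.5 : 1.5. A logistic model with five indicators, standardised to a risk difference, was simulated with 106 per arm (two-arm fit, 60,000 replicates). The simulated variance change v, which includes the cost of fitting, was put into Φ(0.15/(0.0610 × √(1 − v)) − 1.645):

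| Assumed R² | Variance reduction v | Power | Change from 79.2% |
|---|---|---|---|
| 0 | −2.5% | 78.4% | −0.9 |
| 1% | −1.5% | 78.7% | −0.5 |
| 2% | −0.5% | 79.1% | −0.2 |
| 3% | +0.7% | 79.5% | +0.2 |
| 5% | +2.7% | 80.2% | +1.0 |
| 8% | +5.6% | 81.2% | +2.0 |
| 10% | +8.2% | 82.2% | +2.9 |

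(Changes are taken before rounding.) Break-even by interpolation is 2 + 0.5/(0.5 + 0.7) = 2.4%; with one model fitted to all three arms it is about 1.5%. Power counted directly in the same simulation is 0.2 to 0.5 points more favourable (−0.5 at R² 0, +3.2 at 10%). It shows a gain at 2%, where the variance is slightly worse, so that excess is not precision and the variance-based figures are used here.

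The half-width moves from 10.0 points to 1.645 × 0.0610 × √0.973 = 9.9 at R² 5%, and to 1.645 × 0.0610 × √0.918 = 9.6 at 10%.

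Under the assumed pattern, with every factor lowering breastfeeding, R² 5% needs odds ratios of about 3.1 for past low supply and 2.1 for BMI. R² 10% needs about 5.6 and 3.1.

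**The case against.** On the margin: the abstract and the design section both call the trial non-inferiority, and the Sample Size section gives the margin and the one-sided level. A T-test can be run against a null shifted to −15 points, so a sympathetic reader can assemble the intended rule. This stands in part. The ingredients are present and a T-test is not unusable. But the analysis section does not put them together, and it does not say which arm is the reference. A reader might go further and infer that the investigators mean to declare non-inferiority from a non-significant result. The documents do not say that; they are silent, and the 20% in step 3 is what that reading would cost.

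On adjustment: an unadjusted comparison is an accepted default in a randomised trial, and the gain rests on an R² that is nowhere given. Even the sign of the effect changes across the assumed range, and the upper scenarios need strong effects. The protocol calls the five conditions risk factors for low milk supply, not predictors of breastfeeding at 6 months. All of this stands. A reader might infer that leaving out the five factors biases the result or is an error. It is neither, since randomisation makes the unadjusted comparison valid. Nor is adjustment needed to repair enrolment: 109/0.85 gives 129 per group against the planned 125, but that is a separate matter, and the gain is similar at 110 evaluable per arm.

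The margin rule also needs no covariates. Its importance should not be lent to the adjustment.

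**Conclusion.** The main point holds: the 6-month comparison is sized for non-inferiority, and its analysis is not linked to the margin. If the T-test were read against zero, a timing that is truly 15 points worse would pass as no different about 20% of the time, against the intended 5%. This assumes 106 evaluable per arm, a 27% reference rate and a two-sided 5% test. It is a gap in the written rule, not proof that the wrong test will be run.

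Adjustment for the five factors is a small, conditional gain in precision: about −0.9 power points at R² 0, about 0 at 2 to 2.5%, about +1 at 5% and about +3 at 10%, under the assumed prevalences and effect pattern. At most it moves the bound by about 0.4 points against a 15-point margin, so it would seldom change the conclusion.

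**What to change.** **Main change, Analysis Plan.** State that for each early arm minus the 6-or-more-weeks arm (assumed here to be the reference, because none is named) the risk difference in 6-month breastfeeding continuation will be estimated. Non-inferiority is concluded only if the one-sided 95% lower bound lies above −15 points. Say whether any or exclusive breastfeeding is meant, since the Analysis Plan lists both and the Sample Size section does not choose. Replace the two-group wording with the comparisons intended. The cost is wording only.

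**Optional addition.** Record yes/no for all five entry risk factors for every woman, not just the one that qualified her. Give past low supply a separate category for women with no earlier breastfeeding experience, so that they are not mixed with women who breastfed without difficulty. Prespecify a risk difference standardised over these factors, from logistic regression fitted to all three arms, with a degrees-of-freedom-corrected robust or a bootstrap standard error. State which estimate is read against −15 points, and report the unadjusted result alongside. The cost is a few form items and some programming, and about 0.9 power points if the factors are not prognostic. The extra category adds one more term to fit.

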#### *Data and Safety Monitoring*

Patient safety will be monitored continuously by the research team. Given that each of the study interventions is currently considered standard of care at Montefiore, a Data

Safety Monitoring Board is not needed for this trial. The principal investigator and research team will actively review all outcomes for the patients throughout the course of the study, and identify potential adverse events experienced by study participants and report them to the IRB as required by local standards. The PI will be responsible for reviewing these reports and making the final determination of relatedness, reporting to the IRB, and taking relevant actions as needed.

### Adverse Event

An **adverse event** (AE) is any symptom, sign, illness or experience that develops or worsens in severity during the course of the study.

A number of adverse events are expected in the course of the management of labor and postpartum including: pain, bleeding, fevers, chills, nausea, vomiting, diarrhea, dizziness, and endometritis. The only non-serious events that will be specifically collected by the research-team and classified as AEs for this study are those that are both unexpected and considered to be related to study procedures or study drug. All adverse events will be collected, recorded, and assessed locally by the PI or research-team. Events that are determined to be both unexpected and related to the study will be reported and reviewed.

### **Serious Adverse Event**

Adverse events are classified as serious or non-serious. A **serious adverse event** is any AE that is:

- fatal
- life-threatening
- requires or prolongs hospital stay
- results in persistent or significant disability or incapacity
- a congenital anomaly or birth defect
- an important medical event

Important medical events are those that may not be immediately life threatening, but are clearly of major clinical significance. They may jeopardize the subject, and may require intervention to prevent one of the other serious outcomes noted above.

All serious adverse events will be reported to the principal investigator.

### **Adverse Event Reporting Instructions**

Any serious adverse event whether or not it is considered related to the study, will be reported by telephone, email or fax within 24 hours of awareness to principal investigator:

**[name]** Email: [[contact]](mailto:[contact])

The investigator will compile a serious adverse event form and the case will be discussed within 48 hours with the study team. A SAE form will be completed for any SAE that is experienced after the subject has signed the Informed Consent Form.

The Principal Investigator will submit updated SAE. The Principal Investigator will evaluate women who experience a SAE as necessary until the event is resolved.

The principal investigator will report adverse events for review by the IRB per local reporting requirements.

#### Adverse Event Reporting Period

The study period during which adverse events must be reported is normally defined as the period from the initiation of any study procedures to the end of the study treatment follow-up. For this study, the study treatment follow-up is defined as 6 months postpartum.

#### Post-study Adverse Event

All unresolved adverse events should be followed by the investigator until the events are resolved, the subject is lost to follow-up, or the adverse event is otherwise explained. Before discharge, the investigator should instruct each subject to report any subsequent event(s) that the subject, or the subject's personal physician, believes might reasonably be related to participation in this study.

### Study Stopping Rules

If more than 30% of women in any study group have primary lactation failure and are unable to achieve lactogenesis the study will be temporarily stopped and the data reviewed to determine if it reasonable to continue the study.

### *Data Quality*

#### Personnel Selection and Training

The primary investigator and the research team will be responsible to complete the monitoring process as these individuals have experience in the conduct of clinical research and familiarity with research regulations. Furthermore, they are well aware of safety and adverse event review and reporting, the study protocol, the study database, the informed consent forms and processes and this monitoring plan.

#### Frequency

Enrollment will be complete when 375 subjects are enrolled into the trial. Approximately 25 subjects will be enrolled per month. The research team will review the study database and cross check to the medical record for accuracy. Quality assurance will be conducted periodically throughout the study as described below:

- The first time-point of review will occur after the first 5 subjects have been enrolled.
- If no issues of concern are noted, subsequent quality monitoring will occur at least every 6 months by 2 persons on the research team. All findings will be discussed with primary investigator and any concerns will be shared with members of the safety monitoring board.
- The final point of review will be conducted when 100% of the subjects have been enrolled and completed the study.

Additional quality data check may occur on an as-needed basis as determined by the principal investigator.

#### Data Quality Checks

All database entries for all the subjects at each site will be source data verified. Special attention will be given to the following variables and will be 100% source data verified for *all* subjects enrolled in the study.

- Informed Consent
- Inclusion/Exclusion Criteria
- Serious Adverse Events
- Primary Outcomes/Endpoint Data Verification

### Data Management

REDCap (Research Electronic Data Capture) is a secure web application for building and managing online surveys and databases. We will use REDCap software to create data collection forms, generate HIPPA secure web links to the follow-up questionnaire, complete double data entry and manage all data from the study. Only the research coordinators and investigators will have access to the study charts and to the REDCaps database.

### Study Close Out

The principal investigator and research team will conduct the study close out at the time of the final within 3 months after the last patient has completed the study.

The following activities will be completed by the PI to close out the study:

- Ensure all data has been reviewed and collected;
- Ensure all outstanding queries are answered;
- Confirm all Serious Adverse Events, if applicable, have been reported to the IRB(s) and the FDA;
- Ensure all protocol violations were submitted to the IRB per local requirements;
- Ensure that all continuing review reports were submitted to the IRB.

### **Links with Other Projects**

Montefiore is part of the New York City Department of Health and Mental Hygiene's consortium for Quality Improvement Network for Contraceptive Access. Participation in this consortium is an opportunity for hospitals to get support and technical assistance to increase their access to contraception and LARC. Montefiore is a leader in the region, and through this consortium our policies and procedures have been made available to other hospitals seeking to increase contraceptive access. The results of our proposed

study will inform local hospital policies and city initiatives that support breastfeeding while increasing LARC access postpartum.

### Expected Outcomes

The findings from this study will inform clinical practice, national guidelines and policies regarding postpartum use of the etonogestrel contraceptive implant and breastfeeding safety for women at risk for low milk supply.

### Project Timeline

YEAR 1: 2016-2017

	Jul	Aug	Sep	Oct	Nov	Dec	Jan	Feb	Mar	Apr	May	Jun	Jul	Aug	Sep
IRB submission and approval	X	X	X												
Pilot Data Collection Forms			X	X											
Database Development	X	X	X												
Recruitment and Enrollment				X	X	X	X	X	X	X	X	X	X	X	X
6 week follow up					X	X	X	X	X	X	X	X	X	X	X
3 month follow-up							X	X	X	X	X	X	X	X	X
6 month follow-up										X	X	X	X	X	X
Data Entry				X	X	X	X	X	X	X	X	X	X	X	X

YEAR 2: 2017-2018

	Oct	Nov	Dec	Jan	Feb	Mar	Apr	May	Jun	Jul	Aug	Sep	Oct	Nov	Dec
Recruitment and Enrollment	X	X	X	X	X	X									
6 week follow-up	X	X	X	X	X	X	X	X							
3 month follow-up	X	X	X	X	X	X	X	X	X						
6 month follow-up	X	X	X	X	X	X	X	X	X	X	X	X			
Data Entry	X	X	X	X	X	X	X	X	X	X	X	X			
Data Cleaning and Analysis													X	X	
Manuscript Writing													X	X	X
Grant Preparation													X	X	X
